- 5) **For AIT subset only (60 subjects):** an additional volume of blood will be drawn (25 mL for adolescents and 35 mL for adults) to assess CMI (see [Section 7.1.2](#) for detailed instructions regarding the handling of CMI blood samples).

For subjects from subgroup a:

- a. Review for any contraindications, including dengue serostatus at baseline
- b. Perform a physical examination and record the subject's axillary temperature
- c. Urine pregnancy test (pre-injection) (women of childbearing potential only)

- d. Check concomitant medications and record every reportable medication ongoing at the time of vaccination
 - e. Contact IVRS/IWRS to obtain the dose number to be administered
 - f. Inject the appropriate study vaccine into the opposite limb from the limb the vaccination was administered to in Visit 5
 - g. Record the date of injection, the site and side of injection and the route of administration, as well as the dose number of the vaccine
 - h. Affix the vaccine labels in the subject's source documents
 - i. Keep the subject under observation for 30 minutes, and record any injection site reactions or systemic events in the source documents and any reportable concomitant medications
- 6) For subgroup a: Give the subject / subject's parent (s) / legally acceptable representative(s) the DC4 to record any injection site reactions and systemic AEs, together with instructions for its completion, including explanations on the definition and use of intensity scales for collection of AEs.
- For subgroup b: Give the subject / subject's parent (s) / legally acceptable representative (s) the DC4 Group b to collect SAEs until the V07 (Y2) visit
- Dengue seronegative subjects at baseline: Give the subject / subject's parent (s) / legally acceptable representative(s) the MA2
- 7) Remind the parent / legally acceptable representative to bring back the DC4 or the DC4 Group b when they return for the next visit at a specified date
 - 8) Remind the subject /subject's parent(s) / legally acceptable representative(s) to call the study center a serious medical event occurs
 - 9) Arrange an appointment for the next visit (V08 for subgroup a AIT subset; V10 for other subgroup a subjects; V07 Year 2 for subgroup b subjects)
 - 10) Complete the source documents and relevant eCRF pages for this visit

Visit 7–Year 2 (24 Months [+60-day Window] After Visit 5): Booster Vaccination, Collection of Safety Information, and Blood Sample

The Investigator or designated study personnel will:

For subjects from subgroup b:

- 1) Check the information entered into DC4 Group b by interviewing the subject / subject's parent / legally acceptable representative
- 2) Perform a physical examination and record the subject's axillary temperature
- 3) Collect blood sample (BL10, 5 mL) for neutralizing Abs and record the date of collection (see [Section 7.1.1](#) for detailed instructions regarding the handling of blood samples); the volume used for specificity and affinity maturation testing in the AIT subset will also be used from this aliquot as applicable.

- 4) **For AIT subset only (60 subjects):** an additional volume of blood will be drawn (25 mL for adolescents and 35 mL for adults) to assess CMI (see [Section 7.1.2](#) for detailed instructions regarding the handling of CMI blood samples).
- 5) Review for any contraindications
- 6) Urine pregnancy test (pre-injection) (women of childbearing potential only)
- 7) Check concomitant medications and record every reportable medication ongoing at the time of vaccination
- 8) Contact IVRS/IWRS to obtain the dose number to be administered
- 9) Inject the appropriate study vaccine into the opposite limb from the limb the vaccination was administered to in Visit 5
- 10) Record the date of injection, the site and side of injection and the route of administration, as well as the dose number of the vaccine
- 11) Affix the vaccine labels in the subject's source documents
- 12) Keep the subject under observation for 30 minutes, and record any injection site reactions or systemic events in the source documents and any reportable concomitant medications
- 13) Give the subject / subject's parent (s) / legally acceptable representative(s) the DC5 to record any injection site reactions and systemic AEs, together with instructions for its completion, including explanations on the definition and use of intensity scales for collection of AEs.
- 14) Remind the parent / legally acceptable representative to bring back the DC5 when they return for the next visit at a specified date
- 15) Remind the subject /subject's parent(s) / legally acceptable representative(s) to call the study center a serious medical event occurs
- 16) Arrange an appointment for the next visit (V08 for AIT subset; V10 for other subjects)
- 17) Complete the source documents and relevant eCRF pages for this visit

Visit 8 (Visit 7 +7 days [+ 3-day window]): Only for AIT Subset

The Investigator or designated study personnel will:

- 1) Perform a physical examination and record the subject's axillary temperature
- 2) Check concomitant medications and record every reportable medication
- 3) At V08 (Y1) check the information entered into DC4 for subgroup a;
At V08 (Y2) check the information entered into DC5 for subgroup b
by interviewing the subject / subject's parent (s) / legally acceptable representative(s) and request information concerning any medical event, serious or not, that may have occurred since Visit 7

- 4) Obtain a blood sample (BL7 or BL11^a) for neutralizing Abs, Ab specificity (if assessment required) and CMI, and record the date of collection (see [Section 7.1.1](#) for detailed instructions regarding the handling of blood samples)
- 5) Remind the parent / legally acceptable representative to bring back the DC4 (subgroup a) or DC5 (subgroup b) when they return for the next visit at a specified date
- 6) Remind the subject / subject's parent(s) / legally acceptable representative(s) to call the study center if a serious medical event occurs
- 7) Arrange an appointment for Visit 9
- 8) Complete the source documents and relevant eCRF pages for this visit

Visit 9 (Visit 7 + 14 days [+7-day window]): Only for AIT Subset

The Investigator or designated study personnel will:

- 1) Perform a physical examination and record the subject's axillary temperature
- 2) Check concomitant medications and record every reportable medication
- 3) At V09 (Y1) check the information entered into DC4 for subgroup a;
At V09 (Y2) check the information entered into DC5 for subgroup b
by interviewing the subject / subject's parent (s) / legally acceptable representative(s) and request information concerning any medical event, serious or not, that may have occurred since Visit 8
- 4) Check the information entered into DC4 by interviewing the subject / subject's parent (s) / legally acceptable representative(s) and request information concerning any medical event, serious or not, that may have occurred since Visit 8
- 5) Obtain a blood sample (BL8 or BL12^b) for neutralizing Abs, Ab specificity (if assessment required) and CMI, and record the date of collection (see [Section 7.1.1](#) for detailed instructions regarding the handling of blood samples).
- 6) Remind the subject / subject's parent / legally acceptable representative to bring back the DC4 (subgroup a) or DC5 (subgroup b) when they return for the next visit at a specified date
- 6) Remind the subject / subject's parent(s) / legally acceptable representative(s) to call the study center if a serious medical event occurs
- 7) Arrange an appointment for the next visit
- 8) Complete the source documents and relevant eCRF pages for this visit

^a BL7 or BL11: 20 mL will be drawn in adolescent subjects and 30 mL in adult subjects.

^b BL8 or BL12: 20 mL will be drawn in adolescent subjects and 30 mL in adult subjects.

**Visit 10 (Visit 7 + 28 days [+ 7-day window for AIT subset; + 14-day window for all subjects]):
Collection of Safety Information and Blood Sample**

The Investigator or designated study personnel will:

- 1) Perform a physical examination and record the subject's axillary temperature
- 2) Check concomitant medications and record every reportable medication
- 3) At V10 (Y1) check the information entered into DC4 for subgroup a;
At V10 (Y2) check the information entered into DC5 for subgroup b
by interviewing the subject / subject's parent (s) / legally acceptable representative(s) and request information concerning any medical event, serious or not, that may have occurred since Visit 7 or Visit 9
- 4) Record any injection site reactions or systemic events and reportable concomitant medications
- 5) Collect blood sample (BL9 or BL13, 5 mL) for neutralizing Abs and record the date of collection (see [Section 7.1.1](#) for detailed instructions regarding the handling of blood samples). The volume used for specificity and affinity testing in the AIT subset will be used also from this aliquot as applicable.
- 6) **For AIT subset only (60 subjects):** an additional volume of blood will be drawn (15 mL for adolescents and 25 mL for adults) to assess CMI (see [Section 7.1.2](#) for detailed instructions regarding the handling of CMI blood samples).
- 7) Provide MA2 to record any medical events from the booster vaccination, together with instructions for its completion
- 8) Remind the subject / subject's parent(s) / legally acceptable representative(s) to call the study center if a serious medical event occurs
- 9) Complete the source documents, relevant eCRF pages and the termination record for this visit

SAEs and AEs that are related to vaccination or that led to discontinuation:

At any time during the study, a subject who experiences an SAE or an AE must be followed until resolution of the event if *either* of the following is true:

- The SAE or AE is considered by the Investigator to be related to vaccination, and is not resolved by the end of the subject's participation in the trial
- The subject has been discontinued from the trial because of the SAE or AE

Any such subject must be followed until the condition resolves, becomes stable, or becomes chronic.

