--

	
Analysis of covariance (ANCOVA) will be used to compare the post booster mean response of neutralizing Ab levels against each dengue virus serotype of two groups (eg, Group 2 versus Group 1 or Group 3 versus Group 1) controlling for the baseline neutralizing Ab levels against each dengue virus serotype, in subjects seropositive at baseline. Further details regarding the ANCOVA model will be outlined in the SAP.
 
AIT Subset:
 
• For categorical data, the number and percentage of subjects above or equal to the lower limit of detection (LLOD), and the 95% CI of the percentage of the subjects.• For continuous data, Log10: mean and standard deviation; geometric mean, 95% CI of the geometric mean and quartiles, minimum and maximum value.
--	--

Table of Procedures – STAGE I and STAGE II

Visit Number (V)	STAGE I							STAGE II*								
	V01	V02	V03	V04	V05	V06	6M FU (PC7)†	V06_Inf	V07 (Y1)	V07 (Y2)	V08 (Y1/Y2) (AIT only)	V09 (Y1/Y2) (AIT only)	V10 (Y1/Y2)	6M FU (PC)‡		
Trial timelines (Days/Months)	V01	V01+ 28d	V01+ 180d	V03+ 28d	V01+ 365d	V05+ 28d	last inj + 6M		V05+ 12M	V05+ 24M	V07+ 7d	V07+ 14d	V07+ 28d	V07+ 6M		
Time Windows (Days)		+14d	±20d	+14d	±20d	+14d	+20d		+60	+60	+3d	+7d	+14d (+7d for AIT)	+20d		
Informed Consent/Assent	√								√							
Information letter on baseline serostatus								√								
Inclusion/Exclusion Criteria	√															
Demography	√															
Contraindications	√		√		√				Subgroup a: V07 Y1 Subgroup b: V07 Y2							
Significant Medical History	√															
History of YF or JE Infection/Vaccination and/or Dengue Infection	√															
Physical Examination and Temperature§	√	√	√	√	√	√			subgroup a: V07 Y1 subgroup b: V07 Y2		√	√	√			
Urine Pregnancy Test (pre-injection)**	√		√		√											
Concomitant Therapy	√	√	√	√	√	√							√	√	√	
IVRS/IWRS Contact	√		√		√											
Injection	Inj. 1		Inj. 2		Inj. 3				Booster Inj. subgroup a: V07 Y1 subgroup b: V07 Y2							

STAGE I							STAGE II*							
Visit Number (V)	V01	V02	V03	V04	V05	V06	6M FU (PC7)†	V06_Inf	V07 (Y1)	V07 (Y2)	V08 (Y1/Y2) (AIT only)	V09 (Y1/Y2) (AIT only)	V10 (Y1/Y2)	6M FU (PC)‡
Trial timelines (Days/Months)	V01	V01+ 28d	V01+ 180d	V03+ 28d	V01+ 365d	V05+ 28d	last inj + 6M		V05+ 12M	V05+ 24M	V07+ 7d	V07+ 14d	V07+ 28d	V07+ 6M
Time Windows (Days)		+14d	±20d	+14d	±20d	+14d	+20d		+60	+60	+3d	+7d	+14d (+7d for AIT)	+20d

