- 4) **For all subjects:** Collect the fifth blood sample (BL5, 5mL) for neutralizing Abs and record the date of collection (see [Section 7.1.1](#) for detailed instructions regarding the handling of blood samples); the volume used for specificity and affinity maturation testing in the AIT subset will also be used from this aliquot as applicable.
- 5) Give the parent / legally acceptable representative Memory Aid 1 (MA1)
- 6) Remind the parent / legally acceptable representative to have the MA1 with them at the 6 month follow-up telephone contact
- 7) Remind the subject / subject's parent(s) / legally acceptable representative(s) to call the study center if a serious medical event occurs
- 8) Arrange an appointment for Visit 7 (12 months r 24 months [\pm 20-day window] after Visit 5)
- 9) Complete the source documents and relevant eCRF pages for this visit

Telephone Calls: **PC5** (V01 + 14 months [+8-day window]); **PC6** (V01 + 16 months [+8-day window]); **PC7** (V01 + 18 months [+20-day window]); **PC8** (V01 + 20 months [+8-day window]); **PC9** (V01 + 22 months [+8-day window]); **PC10** (V05 + 14 months [+8-day window]), subjects from both subgroups; **PC11** (V05 + 16 months [+8-day window]), subjects from both subgroups; **PC12** (V05 + 18 months [+20-day window]), subgroup a subjects 6-month FUP contact, subgroup b subjects standard phone call contact; **PC13** (V05 + 20 months [+8-day window]), subgroup b subjects; **PC14** (V05 + 22 months [+8-day window] subgroup b subjects); and **PC15** (V05 + 30 months [+20-day window] subgroup b 6-month FUP contact).

- 1) Same procedures as for PC1 and PC2
- 2) Review the information entered into MA by interviewing the subject / subject's parent (s) / legally acceptable representative(s) and request information concerning any medical event, serious or not, that may have occurred since the previous visit or phone call

Visit 6-Inf (unscheduled visit, between PC7 [6 months after last injection in Stage I] and Visit 7–Year 1 [12 Months After Visit 5]): Information of subject on vaccine safety (subgroup a and b)

This unscheduled visit is to take place as soon as possible between V06 and V07. During this visit, subjects will be informed about the increased risk of hospitalized or severe dengue for subjects not exposed to dengue infection prior to the first injection with the CYD dengue vaccine.

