At the latest, this visit will take place at the same time as Y1 V07. In the event the subjects' baseline dengue serostatus is available at the time of V06-Inf, and the Amendment 1 of the protocol is already approved by ECs/IRBs and Health Authorities, subjects could be asked to confirm their willingness to continue participating in the study during this unscheduled visit. If it is not possible to ask for subjects' consent at V06-Inf, subjects will be asked to confirm their participation in the study at Y1 V07.

STAGE II

For each subject, the blood sample collected before first CYD dengue vaccine injection (ie, at V01 for subjects in Group 1, V03 for subjects in Group 2, and V05 in subject in Group 3) will have been assayed with PRNT to determine dengue serostatus at baseline. Only subjects identified as dengue seropositive will be eligible to receive the booster injection.

The blood sample collected 1 year after the last primary series injection will be the last clinical procedure required from dengue seronegative subjects at baseline. Besides the BL6 at Y1 V07, the clinical procedures described hereafter (including the blood samples in the AIT subset) will be for dengue seropositive subjects alone.

One Year Booster (BL6-BL9) or Two Year Booster (BL6; BL10-BL13)

Visit 7–Year 1 (12 Months [+60-day Window] After Visit 5): Booster Vaccination (subgroup a), Collection of Safety Information (subgroup a and b), and Blood Sample (subgroup a and b)

The Investigator or designated study personnel will:

For all subjects:

- 1) Present the changes brought to the study design to the subject / subject's parent (s) / legally acceptable representative(s) in more detail, answer any of his/her/their questions, and ensure that he/she/they has/have been informed of all aspects that are relevant to their decision to continue participating in the study
- 2) Have the subject and / or the subject's parent (s) / legally acceptable representative(s), date and sign the new AF and / or ICF version, as applicable
- 3) Review the pages of the MA with the parent / legally acceptable representative
- 4) **For all subjects having provide their consent:** Collect blood sample (BL6, 5 mL) for neutralizing Abs and record the date of collection (see [Section 7.1.1](#) for detailed instructions regarding the handling of blood samples); the volume used for specificity and affinity maturation testing in the AIT subset will also be used from this aliquot as applicable.

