5.2.7 Contraindications for Subsequent Vaccinations

5.2.7.1 Temporary Contraindications

Should a subject experience one of the conditions listed below, the Investigator will postpone further vaccination until the condition is resolved. Postponement will continue to fall within the timeframe for vaccination specified in the [Table of Study Procedures](#).

- Febrile illness (temperature $\geq 38.0^{\circ}\text{C}$) or moderate or severe acute illness / infection on the day of vaccination, according to Investigator judgment

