12.2 Analysis Sets

12.2.1 Per-Protocol Analysis Set

The Per-Protocol analysis set (PPAS) will include all subjects who had no protocol deviations and will be defined for both stages as follows:

STAGE I:

The subjects who will be vaccinated but who meet any of the following study violations will be excluded from the PPAS in STAGE I:

- Subject did not meet all protocol-specified inclusion/exclusion criteria or definitive contraindications
- Subject did not receive the correct number of doses or injections
- Subject received a vaccine other than the one that he/she was randomized to receive
- Administration of vaccine at V05 was not done as per protocol (site and route of administration)

- Subject did not receive vaccine at V05 in the proper time window defined in the tables of the study procedures
- Subject did not provide a V06 post-dose serology sample in the proper time window
- Subject received a protocol-restricted medication, therapy, or vaccine in STAGE I as defined in Section 6.7.
- Subject's post-injection serology samples at V06 did not produce a valid test result (ie, a result different from "not-reportable" ['NR'] or missing, for at least one dengue serotype)

STAGE II:

The subjects who will be vaccinated but who meet any of the following study violations will be excluded from the PPAS in STAGE II:

- Subject did not meet all protocol-specified inclusion/exclusion criteria or definitive contraindications
- Subject did not receive the correct number of doses or injections
- Subject had negative serostatus at baseline dengue status.
- Subject received a vaccine other than the one that he/she was randomized to receive
- Administration of vaccine at V07 was not done as per protocol (site and route of administration)
- Subject did not receive vaccine at V07 in the proper time window defined in the tables of the study procedures
- Subject did not provide a V10 post-dose serology sample in the proper time window
- Subject received a protocol-restricted medication, therapy, or vaccine in STAGE II as defined in Section 6.7 of the protocol
- Subject's post-injection serology samples at V10 did not produce a valid test result (ie, a result different from "not-reportable" ['NR'] or missing, for at least one dengue serotype)
- Subjects randomized to Group 1 not included in the PPAS in STAGE I

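### Visit 6 step 8 gives Visit 7 a ±20-day window, against 0 to +60 days in the procedures tables and Visit 7 headings; a Year 1 booster given 1 to 20 days early under step 8 would, on the plain reading, leave the Stage II per-protocol set

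*Protocol*

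**What the plan says.** **Step 8.** At Visit 6 (Protocol 5.1.4) the site is told: "Arrange an appointment for Visit 7 (12 months r 24 months". The instruction then gives a plus-or-minus "20-day window] after Visit 5".

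**Headings.** The same section heads the visits "Visit 7–Year 1 (12 Months [+60-day Window] After Visit 5" and "Visit 7–Year 2 (24 Months [+60-day Window] After Visit 5".

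**Tables.** In the row starting "Time Windows (Days", the protocol Table of Procedures and SAP Table 3.1 both print +60 for V07 at Year 1 and at Year 2. The same row prints ±20d for V03 and V05.

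**Which window governs.** Protocol 12.2.1 and SAP 5.2.1 both exclude from the Stage II per-protocol set (PPAS) anyone who meets this condition: "Subject did not receive vaccine at V07 in the proper time window defined in the tables of the study procedures". Protocol 5.2.7.1 also ties postponed vaccinations to the procedures table: "Postponement will continue to fall within the timeframe for vaccination specified in the" table. Protocol 12.2.4 and SAP 5.2.5 use the PPAS for the primary objectives.

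**Rebooking.** Step 9 of Visit 7 Year 1 arranges the next visit: "V10 for other subgroup a subjects; V07 Year 2 for subgroup b subjects".

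**The concern.** A site that follows step 8 may book Visit 7 up to 20 days before V05 + 12 months. In subgroup a, Visit 7 Year 1 is the booster visit. If the booster is given on such a day, the site has followed a protocol instruction and the subject still falls outside the window to which the PPAS rule refers.

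At stake is an avoidable loss from the Year 1 booster non-inferiority analysis. That means the paired test in Group 1a and, only if Stage I non-inferiority is shown (SAP 5.1.1.1), the comparison of Group 2a with Group 1.

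**Working it through.** **Windows compared, in days from V05 + 12 months**

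| | Earliest | Latest | Days allowed |
|---|---|---|---|
| Step 8 | −20 | +20 | 41 |
| Tables and headings | 0 | +60 | 61 |
| Both | 0 | +20 | 21 |
| Step 8 only | −20 | −1 | 20 |
| Tables only | +21 | +60 | 40 |

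The table row writes ± where a window has two sides, so +60 reads as one-sided. The 20 early days are 20/41 = 49% of the days step 8 allows. This is a share of days, not of subjects. The 40 later days do no harm: a booster then stays inside the table window.

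**Who can be affected**

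- Only baseline-seropositive subjects are boosted.
- Subgroup b is rebooked for Year 2 at Visit 7 Year 1, so the point is limited to the Year 1 booster.
- The Stage I PPAS has no V07 timing criterion, so the Stage I tests are unaffected. The full analysis set is unaffected too.

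**Timing.** The inputs are Protocol 5.1.5 (approximate dates; inclusion from 26 April 2016 to August 2016) and the visit windows. 31 August 2016 is assumed as the last inclusion day.

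- Latest V05: 31 Aug 2016 + 365 + 20 days = 20 Sep 2017.
- Latest Visit 6: 20 Sep 2017 + 28 + 14 days = 1 Nov 2017.
- Latest Year 1 Visit 7: 20 Sep 2017 + 12 months + 60 days = 19 Nov 2018.
- Earliest V05, first subject: 26 Apr 2016 + 365 − 20 days = 6 Apr 2017. The table window opens on 6 Apr 2018. Step 8 would allow a visit from 6 Apr 2018 − 20 days = 17 Mar 2018.
- PC8, same subject (V01 + 20 months, +8 days): 26 Dec 2017 to 3 Jan 2018, which is 81 to 73 days before 17 Mar 2018.
- PC9, same subject (V01 + 22 months, +8 days): 26 Feb to 6 Mar 2018, which is 19 to 11 days before 17 Mar 2018. Over all planned V01 dates the shortest PC9 lead is 11 days.

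The protocol text refers to December 2017 (sections 1.2 and 1.3), after the latest planned Visit 6 and before the earliest Year 1 booster. The SAP introduction is dated March 2019, after the latest planned Year 1 booster.

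**The case against.** **Step 8 is leftover wording.** All planned Visit 6 dates precede the December 2017 text, so nobody would be expected to book from this copy of step 8. That stands. Any early appointment would have been made under protocol text we do not have, so its existence is an inference.

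**The operative places are correct.** The booster is given under a heading that states +60 days. It follows new consent, a review of contraindications and serostatus, and an IVRS/IWRS contact. V06-Inf, PC8 and PC9 come before or at that visit. This lowers the chance of an early booster but does not remove the conflict, since none of the steps listed for those contacts is a check of the appointment date.

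**The exclusion may not follow.** The table gives V06 a +14-day window, yet SAP 5.2.1 writes the V06 criterion as ±14 days. If V07 were treated the same way, a booster 1 to 20 days early would stay in the PPAS. The SAP gives no day range for V07, so this cannot be settled from the documents.

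**Stronger readings.** A reader might infer that boosters were given early, that the Year 1 analysis lost power, or that the Year 2 booster is also exposed. The documents show no early booking and give no count from which to derive a loss. The Year 2 appointment is made again at Visit 7 Year 1.

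**Conclusion.** The contradiction is real and sits in current procedural text. Step 8 permits 20 days that the tables and headings do not. On the plain reading of the Stage II rule, a booster on one of those days excludes the subject from the primary analysis of the Year 1 booster.

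The practical weight is small. The number affected is unknown and may be zero, and no power loss is claimed. The conclusion assumes that +60 is one-sided, as the table's notation indicates, and that the PPAS rule is applied to V07 as the table prints it. The calendar rests on approximate planned dates. This is a minor correction held with medium confidence.

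**What to change.** Change step 8 so that Visit 7 is booked at 12 or 24 months after Visit 5 with a +60-day window. This costs one phrase. The headings and tables need no change.

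As of the December 2017 protocol only, send one notice to the 6 sites. It should ask them to check Year 1 Visit 7 appointments at V06-Inf or at the PC8 or PC9 call, and to move any that fall before V05 + 12 months into the 0 to +60-day window. These contacts are already planned, so no visit is added.

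Once the Year 1 boosters are complete, as they would be by the SAP's March 2019 date on the planned calendar, only the text correction remains.
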